12.6.2.1. Summary of Changes and Rationale for Amendment

This is a substantial protocol amendment to:

- Reduce the number of participants in the study from approximately 35 healthy volunteers to approximately 25 healthy volunteers.

This is a non-substantial protocol amendment to:

- Remove some of the exploratory biomarkers.
- Add a spirometry assessment at screening.
- Add a pre-dose pulse oximetry assessment.
- Add continuous ECG telemetry.
- Move the immunogenicity screening sample to Pre-dose in Treatment Period 1.
- Remove height and weight assessments from the follow-up visit.
- Clarify the sequence and priority of assessments.
- Correct typographical errors.

See Section 12.6.2.2 below for a rationale for each change.

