12.6.2.2. List of Specific ChangesProtocol synopsis for study 204987

Protocol synopsis updated to reflect changes in the main body of the protocol.

Section 3: Objectives/Endpoints

Rationale for change: Removal of some of the exploratory biomarkers. SP-D will be analysed and reported, and additional biomarkers may be analysed, as data permit.

Objectives	Endpoints

Exploratory
 
 • To evaluate the effect of a single IV dose of GSK2586881 on ventilatory parameters in healthy volunteers during exercise in hypoxic conditions. • To evaluate the effect of a single IV dose of GSK2586881 on peptide hormone responses to hypoxia and exercise. • To evaluate the pharmacodynamic activity of a single IV dose of GSK2586881 in healthy volunteers during exercise in hypoxic conditions. • To evaluate Pharmacogenetics. 	
 • Change from baseline of oxygen consumption (VO₂), carbon dioxide production (CO₂) and other parameters as data permit. • Baseline levels and changes in response to hypoxia and exercise in kinins (e.g. des-A^{Arg} bradykinin), apelin (e.g. Apelin 13, pyr1-Aelin, 13) and other systems (e.g. dynorphin A) as data permit. • Change from baseline in other biomarkers which may include Atrial Natriuretic peptide (ANP), Brain Natriuretic Peptide (NT-proBNP), Troponin I, Surfactant Protein D (SP-D), IL-6 and/or additional analytes to be determined. • Evaluate I/D polymorphisms in the Angiotensin Converting Enzyme (ACE) gene and analyse the impact on Ang II (and possibly other RAS peptides), hypoxic pulmonary vasoconstriction and responses to GSK2586881 administration.

Section 4.3: Type and Number of Subjects

Rationale for change: The removal of some exploratory biomarkers, led to a re-assessment of the sample size; given that the larger prior sample size was to optimise data collection to include exploratory biomarkers. The sample size has been reduced from 35 to 25 enrolled subjects (30 to 20 completed subjects), because precision estimates show that a difference of between 3 and 5 mmHg in PASP (the primary endpoint) could be detected with an acceptable level of precision based on 20 completed subjects (see Section 9.2).

Approximately ~~35-25~~ subjects healthy volunteers will be randomised such that approximately ~~30-20~~ evaluable subjects complete the study (the target of ~~30-20~~ may be revised following the sample size re-estimation, see Section 9.2.2).

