Rationale for change: The overall sample size has been reduced from 35 to 25 enrolled subjects (30 to 20 completed subjects), so the interim analysis will now be completed after 10 subjects have completed the study, rather than 15.

An interim analysis is planned after approximately **15-10** subjects have completed treatment periods 1 and 2 and the study may be stopped if a reasonable change in PASP is not observed after dosing with GSK2586881 or if review of the safety data suggests a change in the benefit-risk profile. The decision to stop the study will be made by the core members of the GSK study team.

Section 5.4.2: QTc Stopping Criteria

Rationale for change: QTc Stopping Criteria removed from Section 7.2.5, and inserted into Section 5.4 with the other subject stopping criteria.

The same QT correction formula must be used for each individual subject to determine discontinuation from the study. For example, if a subject is eligible for the protocol based on QTcB, then QTcB must be used for discontinuation of this individual subject as well.

A subject that meets either bulleted criterion below will be withdrawn from the study.

- **QTcB or QTcF >500 msec,**
- **Change from baseline: QTc >60 msec**

The QTc should be based on single or averaged QTc values of triplicate ECGs obtained over a brief (e.g. 5-10 minute) recording period.

Section 6.1: Investigational Product and Other Study Treatment

Rationale for change: Order of treatment sequences altered to reflect GSK's standard practice to list placebo first.

Table 1 Description of sequences

Sequence	Period 1	Period 2
AB	GSK2586881 Saline Placebo	Saline Placebo GSK2586881
BA	Saline Placebo GSK2586881	GSK2586881 Saline Placebo

Section 7: Study Assessments and Procedures

Rationale for change: Addition of ventilatory parameters to the list of assessments, and clarification that echocardiograms should be taken as close as possible to the nominal time-point (rather than blood draws), because they are the primary endpoint.

- If assessments are scheduled for the same nominal time, THEN the assessments should occur in the following order:

1. **Ventilatory parameters**
2. Echocardiograms
3. 12-lead ECG
4. vital signs
5. blood draws

Note: The timing of the assessments should allow the ~~blood draw to occur at the exact echocardiogram to be performed as close as possible to the~~ nominal time.

Section 7.1: Time and Events Table

Rationale for change:

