Immunogenicity	X										Treatment period 2 only	
12-lead ECG	X		X							X		
Echocardiogram	X		X		X			X		X	Echocardiogram duration approx 5 min	
Subject enters chamber				X							Subject enters chamber approximately 30 min after study treatment	
Study Treatment (Dosing)		X										
Subject leaves chamber								X			Subject leaves chamber after the fourth echocardiogram, blood samples and vital signs have been taken.	
Exercise challenge						X					For approx 5-10 minutes	
Ventilatory parameters	X		X		X	X ⁴			X		Measurements to be taken at the same time as the 2 min before echocardiograms. During the exercise challenge, an ECG integrated with the ventilatory assessment will be carried out.	
Pulse Oximetry (O ₂ saturation)	<-----→										Will be continuously monitored for safety. A measurement should be recorded at time of each echocardiogram post treatment and databased.	
Telemetry	<-----→										Will be continuously monitored for safety.	

Procedure	Treatment Period 1 and 2 (Washout 3-14 days)										Notes
	Times relative to start of dosing				Hypoxic Challenge ~80 min (Times relative to entry to Chamber)						
	Pre-dose	0h	15 min	15-45 min	0-60 min	60 min	60-70 min	Immediately after exercise	30min rest On exit from chamber	After 30 min rest	
RAS Biomarkers	X	X ¹	X ²	X ³		X ²		X ²	X ⁴	X ²	
Other Biomarkers SP-D	X	X ¹	X ²	X ³		X ²		X ²	X ⁴	X ²	
PK sampling	X	X ¹	X ²	X ³		X ²		X ²	X ⁴	X ²	
AE/SAE review		←-----→									
Concomitant medication review	X										

1. To be taken at the end of exercise-Take at the end of the infusion
2. Taken immediately after echocardiogram.
3. Immediately before entering the chamber
4. To be taken as soon as possible after leaving chamber
5. **On this occasion ONLY, vital signs to be taken after the blood draw.**

Section 7.2.1.3: Follow-up of AEs and SAEs

Rationale for change: Deletion of reference to AEs of special interest, as no AEs of special interest have been defined in the protocol.

After the initial AE/SAE report, the investigator is required to proactively follow each subject at subsequent visits/contacts. All SAEs, ~~and non-serious AEs of special interest (as defined in Section 4.6.1)~~ will be followed until resolution, until the condition stabilizes, until the event is otherwise explained, or until the subject is lost to follow-up (as defined in Section 5.4). Further information on follow-up procedures is given in Appendix 4.

Section 7.2.2: Physical Exams

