7.2.5 QTc Stopping Criteria

- The ~~same~~ QT correction formula ~~must~~ be used for ~~each individual subject~~ to determine ~~eligibility for and discontinuation from the study~~. This formula ~~may not be changed or substituted once the subject has been enrolled~~.
- For example, if a subject is eligible for the protocol based on QTcB, then QTcB must be used for discontinuation of this individual subject as well.
- Once the QT correction formula has been chosen for a subject's ~~eligibility~~, the ~~same formula~~ must continue to be used for that subject ~~for all QTc data being collected for data analysis~~. Safety ECGs and other non-protocol specified ECGs are an exception.
- The QTc should be based on ~~single or averaged QTc values of triplicate electrocardiograms obtained over a brief (e.g. 5-10 minute) recording period~~.

~~A subject that meets either bulleted criterion below will be withdrawn from the study.~~

- QTcB or QTcF > 500 msec,
- Change from baseline: QTc > 60 msec

Section 7.2.5: Clinical Safety Laboratory Assessments

Rationale for change: Correction of typographical errors. Addition of urea to clinical chemistry parameters, to allow the calculation of BUN.

All protocol required laboratory assessments, as defined in Table 2, must be conducted in accordance with the Protocol Time and Events Schedule. Laboratory requisition forms must be completed and samples must be clearly labelled ~~with the subject number, protocol number, site/centre number, and visit date~~. Details for the preparation and shipment of samples will be provided by the laboratory ~~and are detailed in the laboratory manual~~. Reference ranges for all safety parameters will be provided to the site by the laboratory responsible for the assessments.

If additional non-protocol specified laboratory assessments are performed at the institution's local laboratory and result in a change in subject management or are considered clinically significant by the investigator (e.g., SAE or AE or dose modification) the results must be recorded in the CRF.

~~Refer to the SRM for appropriate processing and handling of samples to avoid duplicate and/or additional blood draws.~~

Haematology, clinical chemistry, urinalysis and additional parameters to be tested are listed in Table 2.

Table 2 Protocol Required Safety Laboratory Assessments

Laboratory Assessments	Parameters							
Haematology	Platelet Count	RBC Indices:	WBC count with Differential:					

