3. OBJECTIVE(S) AND ENDPOINT(S)

Objectives	Endpoints
Primary	

 To evaluate the effect of a single IV dose of GSK2586881 on the HPV response in healthy volunteers during exercise under hypoxic conditions. 	
 Change from baseline of Pulmonary Artery Systolic Pressure (PASP) measured via Echocardiography.
Secondary	

 To evaluate the effect of a single IV dose GSK2586881 on RAS peptide responses. To evaluate the safety of a single IV dose of GSK2586881 in healthy volunteers. To evaluate the pharmacokinetics of a single IV dose of GSK2586881. 	
 Effect of GSK2586881 on baseline levels and changes in response to hypoxia and exercise of RAS peptides (e.g. Ang II, Ang(1-7), Ang(1-5)). Vital signs (heart rate, systolic and diastolic blood pressure), oxygen saturation, 12-lead ECGs, AEs, immunogenicity and clinical laboratory assessments and continuous pulse oximetry. Plasma concentrations of GSK2586881 and derived pharmacokinetic parameters.

Objectives	Endpoints

Exploratory
 
 • To evaluate the effect of a single IV dose of GSK2586881 on ventilatory parameters in healthy volunteers during exercise in hypoxic conditions. • To evaluate the effect of a single IV dose of GSK2586881 on peptide hormone responses to hypoxia and exercise. • To evaluate the pharmacodynamic activity of a single IV dose of GSK2586881 in healthy volunteers during exercise in hypoxic conditions. • To evaluate Pharmacogenetics 	
 • Change from baseline of oxygen consumption (VO₂), carbon dioxide production (CO₂) and other parameters as data permit. • Baseline levels and changes in response to hypoxia and exercise in kinins (e.g. des-Arg-bradykinin), apelin (e.g. Apelin 13, pyrl-Apelin, 13) and other systems (e.g. dynorphin A) as data permit. • Change from baseline in other biomarkers which may include Atrial Natriuretic peptide (ANP), Brain Natriuretic Peptide (NT-proBNP), Troponin I, Surfactant Protein D, IL-6 and/or additional analytes to be determined. • Evaluate I/D polymorphisms in the Angiotensin Converting Enzyme (ACE) gene and analyse the impact on Ang II (and possibly other RAS peptides), hypoxic pulmonary vasoconstriction and responses to GSK2586881 administration.

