7.1. Time and Events Table

7.1.1. Screening and Follow up

Procedure	Screening ¹ (up to 28 days prior to Treatment Period 1, Day 1)	Follow up (7- 10 days post lastdose)	Notes
Informed consent	X		
Inclusion and exclusion criteria	X		
Demography	X		
Full physical exam including height and weight	X	X	Weight at screening will be used for dosing calculation.
Alcohol, DoA , Smoking test	X		
Medical history (includes substance usage [and family history of premature CV disease])	X		Substances: [Drugs, Alcohol, tobacco]
Past and current medical conditions [including cardiovascular medical history]	X		
[Serum OR urine] pregnancy test (WCBP)	X		
HIV, Hep B and Hep C screen	X		
Laboratory assessments (include liver chemistries	X	X	Non Fasting
Immunogenicity	X	X	
12-lead ECG)	X	X	Triuplicate ECG required at screening.
Vital signs)	X	X	Triuplicate vital signs required at screening.
Echocardiogram	X		
Concomitant Medication review	X	X	
Hypoxia chamber plus exercise	X		Tolerance to 4000m for 10 mins followed by followed by incremental exercise testing to determine maximum oxygen uptake (VO2max) and calculate 70% of VO2max for the exercise challenge d
Pharmacogenetic sample (PGx)	X		Can be taken any time after consent has been signed. Only required once and is optional.
AE/SAE review	X	X	As per timings detailed in Section 7.2.1.1

1. Screening assessments are allowed to be conducted on more than one day

7.1.2. Treatment Period 1 and 2

Procedure	Treatment Period 1 and 2 (Washout 3-14 days)										Notes
	Times relative to dosing				Hypoxia (Times relative to entry to Chamber)						
	Predose	0h	15 m	15-45m	0-60m	60m	60-70m	Immediately after exercise	30m rest on exit from chamber	After 30 mins rest	
Randomisation	X										Randomisation can occur up to the day before the first treatment period
Brief physical exam	X										
Vital signs	X		X					X		X	
Immunogenicity	X										Treatment period 2 only
12-lead ECG	X		X							X	
Echocardiogram	X		X		X			X		X	Echo duration approx 5 mins
Subject enters chamber				X							Subject enters chamber approximately 30 minutes after study treatment
Study Treatment (Dosing)		X									
Subject leaves chamber							X				Subject leaves chamber after the fourth echocardiogram and vital signs have been taken.
Exercise challenge						X					For approx 5-10 minutes

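### No safety laboratory panel is scheduled between the two doses, so the liver stopping rule has no planned trigger before the only remaining dose, and the laboratory endpoint has no panel after a single treatment in completers

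*Protocol*

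**What the plan says.** In Section 7.1.1 the row "Laboratory assessments (include liver chemistries" is ticked at screening (at most 28 days before Day 1 of Period 1) and at follow-up (7-10 days after the last dose). The table in Section 7.1.2 covers vital signs, ECG, echocardiography, ventilatory measures, oximetry, biomarkers, PK and immunogenicity. It has no row for haematology, chemistry or urinalysis. Amendment 02 reproduces both tables in Section 12.6.2.2. Its table headed "Treatment Period 1 and 2 (Washout 3-14 days)" has no such row either, and its laboratory row in the screening and follow-up table keeps the same two ticks.

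The section on clinical safety laboratory assessments adds no time points of its own. The tests "must be conducted in accordance with the Protocol Time and Events Schedule".

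Two other provisions depend on these data:

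- **Liver stopping rule.** The liver chemistry stopping criteria (Section 5.4.2 in Amendment 01; Appendix 2) end study treatment for a subject who meets them, and Section 5.4.2.1 rules out a restart.
- **Secondary endpoint.** In Section 3 the secondary safety endpoint includes "immunogenicity and clinical laboratory assessments and continuous pulse oximetry".

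Immunogenicity, which is part of the same endpoint, does have a pre-dose sample marked "Treatment period 2 only" in the Amendment 01 table. Amendment 02 changes only the first sample: "Move the immunogenicity screening sample to Pre-dose in Treatment Period 1".

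**The concern.** Each subject receives at most two doses, so once Period 1 has been dosed, the only administration a stopping rule can prevent is the Period 2 dose. A rule based on ALT needs an ALT result between the doses, and the schedule provides none. The rule then acts only if someone orders an unscheduled test.

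The same gap affects the laboratory endpoint. In a completer, the single scheduled post-dose panel comes after drug, saline and two hypoxia and exercise challenges. The crossover, which Section 4.4 justifies by letting subjects serve as their own controls, gives no such control for laboratory values. An analysis plan cannot supply a sample that was never drawn, so this has to be settled in the protocol's schedule.

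**Working it through.** The plan gives no figure to reproduce here. The check is interval arithmetic on its stated windows, followed by the precision that one added panel would give.

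**Inputs**
- Screening: up to 28 days before Period 1 (Section 7.1.1).
- Washout: 3-14 days (Sections 4.2 and 7.1.2), read as the interval between doses.
- Follow-up: 7-10 days after the last dose (Section 7.1.1).
- Completers: about 20. Amendment 02, on Section 4.3, states: "The sample size has been reduced from 35 to 25 enrolled subjects (30 to 20 completed subjects)".

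**Scheduled panels in a completer**
- Between the Period 1 dose and the Period 2 dose: 0.
- After any dose: 1, following both treatments.

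**Age of the last scheduled liver panel at the Period 2 dose**
- Maximum = screening window + longest washout = 28 + 14 = 42 days.
- In the placebo-first sequence that dose is active drug. In the drug-first sequence it is saline, followed by the second hypoxia and exercise challenge.

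**Time from active drug to the only post-dose panel**
- Drug-first: 3 + 7 = 10 days to 14 + 10 = 24 days.
- Placebo-first: 7 to 10 days.

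By follow-up both sequences have received drug and saline. Comparing them contrasts treatment order and time since drug; it does not contrast drug with placebo. The change from screening to follow-up can span 28 + 14 + 10 = 52 days and covers both treatments and both challenges.

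**What a panel at Period 2 pre-dose would give**
- It falls 3-14 days after the first treatment, or 2-13 days if drawn the day before.
- With equal allocation it compares 20/2 = 10 drug-first with 10 placebo-first completers.
- Unadjusted 95% half-width in SD units: t(0.975; 18) × √(2/10) = 2.101 × 0.447 = 0.94.
- Adjusted for the screening value, with an assumed correlation r (the documents give none): t(0.975; 17) × √[(2/10)(1 − r²)], where t = 2.110.
  - r = 0.3: 0.90
  - r = 0.5: 0.82
  - r = 0.7: 0.67
- If none of 10 drug-first subjects has an abnormality, the one-sided 95% upper bound on incidence is 1 − 0.05^(1/10) = 0.26.

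**The case against.** The strongest reply is that this is a proportionate schedule for a small Phase I study.

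- The dose of 0.8 mg/kg lies within the 0.1-1.2 mg/kg single-dose range already given to healthy subjects (Section 4.5), and the risk table in Section 4.6.1 names no hepatic, renal or haematological risk.
- The comparator is saline, so asking whether drug or placebo caused a laboratory change is hardly a live question.
- Sections 7 and 7.2 let the sponsor add laboratory time points without an amendment, and adverse events are reviewed with a causality assessment.
- The added panel would be imprecise and would miss changes that resolve before the draw.

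Much of this stands, and it is why the point is minor. A reader might infer that the laboratory endpoint is defeated because changes cannot be attributed to either treatment. The documents do not support that. They specify no drug-versus-placebo laboratory contrast and no formal hypothesis (Section 9.1), and every completer has received active drug before the follow-up panel, so a persisting effect could still be seen. A reader might also infer that no laboratory data after a single treatment can exist. That goes too far as well: Section 5.4 has subjects who withdraw undergo the planned follow-up procedures where possible, so a subject leaving after Period 1 may contribute such a panel.

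The reply does not answer the liver rule. Extra time points are optional and depend on newly available data, so they do not provide a planned ALT before Period 2. The earlier healthy-subject single doses are described as given over 30 minutes, whereas Section 6.1 infuses this one over 3-5 minutes, so the prior experience does not fully cover the regimen.

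**Conclusion.** The point holds as a minor design weakness. The liver stopping rule is the stronger half: in completers no scheduled test can trigger it before the one dose it could still prevent, and the last scheduled liver panel may be 42 days old by then. That figure is the joint maximum of two windows, not a typical value. It would be wrong to read this as leaving subjects without protection, because unscheduled tests and adverse-event review remain available.

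The endpoint half is weaker. Completers have no scheduled panel after one treatment only, and the sequence comparison at follow-up reflects time since drug (10-24 against 7-10 days).

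The conclusion rests on the tables in Amendment 01 and on those reproduced in the Amendment 02 change list. The clean Amendment 02 body is not in the part reviewed. The precision figures assume 20 completers split equally, and the adjusted ones also assume correlations of 0.3 to 0.7. The primary PASP analysis is not affected.

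**What to change.** Add one row to the treatment-period table: a safety laboratory panel including ALT and bilirubin at Period 2 pre-dose, drawn with the PK, biomarker and immunogenicity samples already taken then, or the day before. Require the liver results to be reviewed against the stopping criteria in Appendix 2 before the Period 2 dose. Refer to Appendix 2 by name, because Amendment 02 now lists "Section 5.4.2: QTc Stopping Criteria" under the number that Amendment 01 used for the liver criteria. Report the comparison after the first treatment descriptively, with its interval.

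The cost is one tube per subject within the 500 mL limit in Section 7. Draw volumes are in the SRM, so the fit must be checked there. The liver review also needs same-day turnaround or a day-before draw. Post-dose intervals will not match: 3-14 days after the first dose (2-13 if drawn the day before) against 7-10 days after the second. The panel does not give a full within-subject contrast, and changes that resolve before the draw stay unseen.

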7.2. Safety

Planned time points for all safety assessments are listed in the Time and Events Table (Section 7.1). Additional time points for safety tests such as vital signs, physical exams and laboratory safety tests may be added during the course of the study based on newly available data to ensure appropriate safety monitoring.

7.2.1. Adverse Events (AE) and Serious Adverse Events (SAEs)

The definitions of an AE or SAE can be found in [Appendix 4](#).

The investigator and their designees are responsible for detecting, documenting and reporting events that meet the definition of an AE or SAE.

